My long-term goal is to promote successful aging among persons with chronic HIV-1 infection by strategies to optimize physical function and minimize disability and frailty. The primary objective of this proposal is to investigate the GH/IGF-I axis as a potential pathway of early functional impairment in persons aging with HIV. My research is anticipated to advance understanding of the mechanisms and interactions of the GH/IGF-I axis in physical function. My central hypothesis is that a phenotype of accelerated functional impairment observed among some persons with HIV infection will be associated with disruption in the GH/IGF-I axis (the somatopause). This hypothesis will be evaluated through the following specific aim:

**Specific Aim 1: Determine the impact of high or moderate intensity combined resistance (REx) and cardiovascular exercise (CEx) on physical function in older HIV+ (n=36) and HIV- (n=36) adults.**

Approach: Previously sedentary older adults (aged 50-75 years) will undergo a 24 week REx + CEx exercise training intervention.

Hypothesis 1a: Both HIV+ and HIV- older adults will have a significant improvement in physical function (chair rise time) with REx + CEx, but HIV+ will have a *lower* increase than HIV- older adults.

Hypothesis 1b: Both HIV+ and HIV- older adults randomized to a high intensity REx + CEx intervention will have greater improvement in physical function than those randomized to the moderate intensity exercise.

Hypothesis 1c: Utilizing established techniques for screening and training, moderate intensity exercise followed by randomization to either continue a moderate- or progress to high- intensity exercise will result in minimal or no adverse events and will result in similar completion rates, with 80% of participants completing the training program.

**Specific Aim 2: Determine the impact of high or moderate intensity combined REx and CEx on local and systemic IGF-I, as an explanatory factor in the physical function changes of older HIV+ and HIV- adults.**

Approach: Previously sedentary older adults (aged 50-75 years) will undergo a 24 week REx + CEx exercise training intervention.

Hypothesis 2a: HIV+ older adults will have lower *systemic* IGF-I at baseline and at week 20 compared to HIV- adults, with blunted response to exercise training.

Hypothesis 2b: HIV+ older adults will have lower baseline and lower week 20 *skeletal muscle* IGF-I mRNA and IGF-I protein, compared to HIV- adults

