#### **IV. Research Methods**

##### **A. Outcome Measure(s):**

The objectives of this study are to

- 1) demonstrate an improvement in physical function among HIV+ and HIV- older adults,

- 2) determine whether differences exist in the responsiveness of the GH/IGF-I axis to an exercise stimulus in treated HIV infection, and, if so, whether these differences mirror those of aging (decreased IGF-I), or are unique to HIV, and
- 3) determine whether exercise results in a reduction in inflammatory and activation markers both acutely and chronically
- 4) determine whether these responses have a dose-response to exercise intensity such that a higher intensity intervention is associated with a greater improvement in function.
- 5) explore barriers and facilitators to exercise maintenance.

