## C. Study Design and Research Methods

Potentially eligible subjects will be screened during routine clinic visits or over the telephone. Potentially eligible and interested subjects will return for informed consent and a screening/baseline visit. No research procedures will occur prior to consent, including the MOCA.

After obtaining informed consent, participants will undergo a graded exercise test to screen for potential underlying cardiovascular disease. V02 peak will be measured at this time to develop the exercise prescription. All participants will begin with a low intensity lead-in for 1-2 weeks, then advance to a moderate intensity exercise during first 12 weeks. Randomization to continue on moderate versus advance to high intensity will occur at week 13.

**1. Consent & baseline visit.** After obtaining consent, the participant will be evaluated

-After obtaining consent, the participant will be evaluated by

- medical history, physical examination including vital signs
- Montreal Cognitive Assessment (MOCA)
- Resting BP, 12-lead resting ECG, and then a graded exercise test (GXT) administered by research personnel and a clinician experienced in exercise stress testing of older adults ([name]) to screen out volunteers with evidence of ischemic heart disease, serious arrhythmias, or abnormal HR/BP responses to exercise. Briefly, the test will begin at a comfortable walking speed and 0% elevation; speed will be maintained and the grade increased by 2% every 2 min, until the participant reaches 85% of age-predicted maximal heart rate or the test is otherwise terminated. The absolute and relative indicators for terminating an exercise test that are recommended by the American College of Sports Medicine (ACSM) will be employed.
- Baseline physical function assessments will be administered.

**2. Procedure visit #1 (within 14 days of visit #1).** All participants will arrive between 7:30-8am for:

- DXA scan
- Vital signs
- Anthropometrics (waist/hip circumference)
- Blood draw (fasting)
- 36 (up to 46, if needed to ensure 36 paired biopsy samples) volunteer participants (18 HIV+/18 HIV-) will have a muscle biopsy
  - If muscle biopsy at the end of the study cannot be done (patient refuses, change in medications, etc), then the number of biopsies will increase to a maximum of 46 in order to ensure each group has at least 18 paired (entry/completion) biopsy samples.
- Questionnaires

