**1. Muscle biopsy.** Subjects participating in the muscle biopsy portion will have a biopsy prior to beginning the exercise intervention and after completing the 24 week intervention. Subjects will be advised to refrain from any physical activity for at least 48 hours following the biopsy and return within 14 days of the screening/consent visit. Non-steroidal anti-inflammatories or aspirin are held for 7 days prior to the biopsy. If participants are taking direct oral anticoagulants, this will be held for 48 hours prior to the procedure (72 hours if creatinine clearance is 30-50 and taking dabigatran). Therapy can be resumed 24 hours after the procedure, or as instructed by their physician. At study completion, subjects will be asked to return within 7 days of the final exercise session for a muscle biopsy. The exercise intervention will begin >24 hours after the initial biopsy, but within 14 days. Participants will be asked to abstain from alcohol or caffeinated beverages after 1300h and to fast from any food or drink beginning at 9pm with the exception of water. Subjects will arrive at 8am in the CTRC for the biopsy. Percutaneous samples of the vastus lateralis muscle will be obtained. After cleansing the area of the thigh with antiseptic (e.g., chlorhexidine, Betadine solution), 1% lidocaine (without epinephrine) will be injected under the skin. A 3-5 mm incision will be made in the skin and fascia over the belly of the vastus lateralis, and 100-150 mg of muscle tissue will be removed using a Bergstrom side-cutting biopsy needle with suction applied. The incision will be closed and a compression wrap and ice will be applied to the incision area for 20 minutes. The patient will be given instructions for wound care before discharge.

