**Muscle specimen processing.** Tissue specimens will be immediately placed in RNase free vials, immersed in liquid nitrogen, and then stored at -80°C for batch analysis. Frozen tissue will be homogenized using a MagNA Lyser system (Roche Molecular Systems, Branchburg, NJ). Total RNA will be extracted from the supernatant using the Trizol Plus RNA Purification Kit (Life Technologies, Carlsbad, CA). RNA quantity and quality will be determined by spectrophotometry (NanoDrop ND-1000, Thermo Scientific, Rockford, IL). Total DNA will be measured using the MagnaNA Pure LC DNA Isolation kit (Roche Applied Science). mtDNA and genomic DNA in muscle tissue will be assayed by RT-PCR using standard curves generated using plasmid controls for both mtDNA and nuclear genes as described previously[138]. The number of mtDNA genome copies per cell for muscle, which is multi-nucleated, will be calculated.

**Skeletal muscle analyses.** Total RNA will be reverse transcribed and amplified using the TaqMan RNA to CT 1-Step Kit and TaqMan Gene Expression Assays (primers and probes; Life Technologies). mRNA from the following genes will be measured: IGF-1, androgen receptor (AR), mechano growth factor (MGF), SOCS-3, *PGC-1α*, *IL-6R*, *TNFR1*, *TNFR2*, *MFN-1*, *MFN-2*, and *FIS-1* mRNA. Gene-specific assays will be plated into triplicate wells of 96-well plates with serial dilution of GAPDH as reference for cross plate comparison and no-template controls for each gene. Reactions will be run using a real-time PCR detection system (Bio-Rad; Hercules, CA). Validation experiments will be performed to demonstrate that efficiencies of target and reference genes are approximately equal. The target genes will be normalized to GAPDH RNA concentrations to control for sample degradation and other factors that could reduce quantitative PCR efficiency. Linear regression will be used to determine the relationship of relative target RNA concentrations, including high-, medium- and low-abundance mRNAs, determined by real-time RT-PCR to the relative abundance of specific gene sequence reads in RNA-seq. Differences in selected gene expression will also be tested using two-way ANOVAs with the target gene as the dependent variable, intervention timing (before or after) and HIV serostatus (infected or uninfected) as independent variables.

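### The muscle gene-expression ANOVA has no exercise-intensity term, so it gives no estimate of the randomised high v moderate contrast, and Section F does not clearly supply one

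*Combined protocol and SAP*

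**What the plan says.** **Aims.** The title of Specific Aim 2 is to "Determine the impact of high or moderate intensity combined REx and CEx on local and systemic IGF-I". The muscle hypothesis beneath it, 2b, is a contrast by HIV status only: "HIV+ older adults will have lower baseline and lower week 20" muscle IGF-I mRNA and protein than HIV- adults. The fourth objective in Section IV.A is to "determine whether these responses have a dose-response to exercise intensity", where the preceding objectives include the response of the GH/IGF-I axis.

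**Muscle analysis.** Section IV.D.1 lists 11 transcripts: IGF-1, AR, MGF, SOCS-3, PGC-1α, IL-6R, TNFR1, TNFR2, MFN-1, MFN-2 and FIS-1. It then states: "Differences in selected gene expression will also be tested using two-way ANOVAs with the target gene as the dependent variable", with "intervention timing (before or after) and HIV serostatus (infected or uninfected) as independent variables". No other factor is named.

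**Section F.** The mixed model compares groups by HIV status and, in parallel, by exercise intensity. Exercise intensity is one of the covariates that the primary analysis will consider. A separate sentence makes change in IGF-I mRNA a primary outcome in the biopsy subset.

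**Samples.** The biopsy subset is "36 (up to 46, if needed to ensure 36 paired biopsy samples) volunteer participants", planned as 18 HIV+ and 18 HIV-. Each has a "biopsy prior to beginning the exercise intervention and after completing the 24 week intervention". Randomisation to intensity takes place at week 13, with 18 moderate and 18 high planned in each HIV group of 36.

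**The concern.** Intensity is the only randomised factor in the trial. The HIV comparison is between recruited groups, so the high v moderate contrast is the only one that carries the protection of randomisation. The ANOVA omits that factor, even though arm is known for every participant with a completion biopsy.

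Two things are at stake. First, for genes other than IGF-I, following the text as written would yield no intensity estimate at all. Second, muscle IGF-I mRNA, a primary outcome in the subset, falls under two descriptions of the analysis that are not tied together: one without intensity and one in which intensity may or may not appear. The choice between them would be made after the data are in hand.

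**Working it through.** **1. What the ANOVA can estimate.** With post = 1 for the completion sample, the stated factors and their interaction give

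mean expression = μ + α·post + β·HIV + γ·post×HIV.

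Hypothesis 2b is carried by β (baseline) and β + γ (after training). No parameter separates high from moderate. The baseline biopsy precedes randomisation, so arm can act only on the completion sample. The missing term is δ·post×high, and δ is the high v moderate difference in change.

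**2. Whether Section F supplies δ.**
- For IGF-I mRNA: possibly. Intensity groups are evaluated there and the outcome is named there, but the mixed model is not stated to apply to it and the intensity adjustment is conditional.
- For the other 10 listed transcripts (11 − 1): no. Section F names none of them, so the ANOVA is the only group comparison given.

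**3. Check of the power method on the plan's own figure.** The documents give no power figure for the muscle analysis. For chair rise, Section F claims over 80% with 29 per group, a difference of 1.5 s, SD 2.0 s and two-sided α of 0.05. The standardised difference is 1.5/2.0 = 0.75 and the noncentrality is 0.75 × √(29/2) = 2.86. The noncentral t distribution then gives 80.1% power, so the plan's figure reproduces.

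**4. Precision of the added contrast.** The same method is solved for the standardised difference in change at 80% power, with noncentrality d × √(n/2). An even arm split is assumed, and the paired samples are analysed as within-person change.

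| Comparison | n per arm | Detectable d | Noncentrality |
|---|---|---|---|
| HIV groups pooled | 18 v 18 | 0.96 SD | 0.96 × √9 = 2.88 |
| Within one HIV group | 9 v 9 | 1.41 SD | 1.41 × √4.5 = 2.99 |

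**5. Effect on the HIV contrast.** These figures need an intensity effect e, in within-arm SDs of the change. The documents give none; 0.5 to 1.0 is assumed.
- *Residual variance.* With an even split, omitting the term inflates the variance of the change by 1 + e²/4, which is 1.06 at e = 0.5 and 1.25 at e = 1.0.
- *Chance imbalance.* Only a difference in intensity mix between the HIV groups shifts the HIV contrast; an uneven split shared by both groups does not. If 18 of 36 are biopsied in each group without regard to arm, the number on high intensity has SD √(18 × ½ × ½ × 18/35) = 1.52. The two groups then differ by 4 or more participants with probability 0.10, or 0.06 if the 18 come from 29 completers. A gap of 4 shifts the contrast by (4/18) × e = 0.11 to 0.22 SD. Averaged over randomisation the shift is zero, provided biopsy completion is unrelated to arm.

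**The case against.** The strongest defence has four parts.

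- **The plan does not ignore intensity.** Section F evaluates intensity groups and names change in IGF-I mRNA, the muscle outcome closest to Aim 2. This stands in part. A reader might infer from the ANOVA that Aim 2's intensity question has no analysis anywhere in the plan. The documents do not support that; they support only that the link is not stated and the adjustment is not definite.
- **The ANOVA fits Hypothesis 2b.** This stands. The hypothesis is an HIV contrast and the ANOVA addresses it. No numbered hypothesis predicts an intensity effect on a muscle gene, and the dose-response objective goes on to speak of improvement in function. But the title of Aim 2 does ask about intensity and local IGF-I.
- **The ANOVA is supplementary.** It is described as an additional test, within a laboratory-methods section. That lowers the stakes. It does not fill the gap for the genes that have no other group comparison.
- **The added contrast has little power and multiplies tests.** True, as step 4 shows. This is a reason to report it as an estimate with an interval, not a reason to leave out a known randomised factor.

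A reader might also infer that the HIV comparison is confounded by intensity. That is not supported. Allocation is planned 1:1 within each HIV group, only completion samples can be affected, and the expected bias is zero under the condition in step 5.

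**Conclusion.** The point holds as a gap in specification. The ANOVA cannot estimate the high v moderate contrast. Section F may do so for IGF-I mRNA but does not commit to it, and no intensity comparison is written for the other listed genes. It is an inexpensive improvement; it does not undermine the HIV comparison or Hypothesis 2b.

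The gain is modest: an unbiased but imprecise randomised estimate, with about 0.96 SD detectable when the HIV groups are pooled. That figure assumes 36 complete pairs split evenly by arm and analysed as within-person change. Removal of any chance difference in intensity mix between the HIV groups is a side benefit only, and its size rests on an assumed intensity effect.

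**What to change.** Use one model in Section IV.D.1 and for the Section F analysis of change in IGF-I mRNA, and state that it governs both. Its terms are timing, HIV status, timing-by-HIV, and randomised intensity acting only on the completion sample (the timing-by-intensity term). Make the intensity term definite in both places.

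Report the intensity contrast with its confidence interval beside the HIV contrast. Label it exploratory for genes other than IGF-I, and say where MGF belongs, since the Background treats it as an IGF-I splice variant. State that with about 18 v 18 pairs only differences near 0.96 SD are detectable at 80% power.

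The change needs no new visits, samples or assays. It costs one degree of freedom, or two if a main effect of intensity is also fitted. It also adds low-power contrasts: across 10 exploratory genes with no true effect, 10 × 0.05 = 0.5 nominally significant results would be expected. The emphasis should therefore be on estimates and intervals rather than tests.

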#### **B. Description of Population to be Enrolled:**

Participants will be sedentary men and women between the ages of 50 and 75 years (*performing < 2 days/week of 30 minutes of CEx or REx during the prior 6 mo*). HIV+ subjects will initially be recruited from the University of Colorado Infectious Diseases Group Practice which provides care for approximately 1700 HIV+ adults, with 528 patients aged 50-59, 170 patients aged 60-69, 25 patients aged 70-79. Subjects will be on effective ART for a minimum of 2 years with HIV-1 viral load primarily below the limit of detection with no HIV RNA >200 copies/mL. Recruitment of HIV- subjects will first target high risk HIV- partners, friends, or family members of HIV+ subjects, current research participants of IMAGE (Investigations in Metabolism, Aging, Gender and Exercise) research group, the Internal Medicine Clinic, and the Family Medicine Clinic. Inclusion and exclusion criteria were selected to enroll the most appropriate study population while maximizing the generalizability of the findings.

- Inclusion:
  - Between the ages of 50-75 years at study entry
  - HIV+ subjects must be on an ART regimen (change in regimen permitted for preference/tolerability but not for virologic failure) for a minimum of 2 years, with a viral load < 200 during that 2 year period
    - Initial recruitment will target those on ART for at least 5 years; this will be removed as needed to achieve target sample size
  - Sedentary (< 2 days/week of CEx and/or REx over the prior 6 months)
  - CD4 T-cell count greater than 200 cells/mm^3
  - All participants must be able to perform activities of daily living without assistance, and ambulate independently.
  - BMI  $\geq$  20 and <40 (initial goal, will expand if difficulties recruiting)
  - Among females, must be post-menopausal (no menses for >12 months, or if prior hysterectomy, FSH >30 IU/l)
- Exclusion criteria:
  - Due to interaction with the GH/IGF-I axis, persons **with diabetes with a hemoglobin A1c >7%, on insulin, on GLP-1 analog, or DPP IV inhibitors. Well-controlled diabetics on other oral medications with hemoglobin A1c of 7.5 or less are eligible.**
  - Persons on growth hormone or growth hormone axis therapy (i.e., tesamorelin) will be excluded.
  - Post-menopausal use of stable doses of estrogen/progesterone (at least 3 months) will be permitted.

- Persons on intramuscular testosterone will be excluded; stable doses of patches or gel will be permitted

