- Participants on anticoagulants (clopidogrel, Coumadin, etc) will be excluded from the muscle biopsy. Patients on short-acting anticoagulant therapy requiring dose cessation for only 48-72 hours (rather than 1-2 weeks for clopidogrel or Coumadin) for can be considered for muscle biopsy with approval by their hematologist or treating physician.
- Aspirin and Non-steroidal anti-inflammatory agents are not exclusions but should be stopped 1 week prior to biopsy.
- For the substudy only, participants experiencing a diarrheal change in bowel habits consisting of greater than one loose stool a day within the last two weeks will be excluded. Patients with chronic loose stools will be included.
- Focus Group Substudy will be more inclusive, as participants will only be participating in a group meeting and not exercising as part of the study:
  - Inclusion:
    - Age 50 or older at study entry
    - Either 1) currently exercising 2 days/week or more, or sedentary  $< 2$  days/week of CEx and/or REx over the prior 6 months
    - Willing to participate in a group discussion with other HIV-infected individuals
    - HIV-infected for at least 2 years.
  - Exclusion criteria:
    - Non-English speaker (group discussions will be in English only)
    - Unable to participate in any form of exercise. Participants with severe activity limitations will still be eligible, as they could still participate in balance training, band resistance, etc.
    - Unable to provide own consent.
    -

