**Muscle protein expression.** The protein expression of IGF-1, IGF receptor, IL-6R, SOCS-3, TNFα, TNFR-1, NF-*κB* and MuRF1; *PGC1-α* and Mitochondrial Transcription Factor (mt biogenesis), citrate synthase (mt function); *Mfn-1* and -2, *Opa1*, *FIS-1* and *Drp1* (mt fusion/fission) will be measured by established Western Blot techniques[139] using commercially available antibodies (Cell Signaling Technology, Inc., Beverly, MA).

**Risks:** The risks associated with muscle biopsy include brief, mild burning pain from the local anesthetic (lidocaine), more than mild discomfort during the acquisition of tissue (about 10% of cases), and infection (less than 0.4% of cases). Allergy to the anesthetic (skin swelling or rash) occurs rarely. There may be persistent numbness in the biopsy area.

**Plan to Minimize Risk:** Risks of the muscle biopsy procedure will be *minimized* by having a trained clinician perform the procedure on participants who meet the biopsy-specific criteria listed above. As part of her career development award, [name] is obtaining the skills in muscle biopsy. She is currently being trained in the procedures and will not begin performing the biopsies until her skills have been approved by an experienced clinician ([name] and/or [name]) with expertise in muscle biopsies. Participants will be observed following the procedure for any adverse events and given strict instructions for wound care. A phone call will be made within 48 h of the biopsy procedure to assess wound healing with a study clinician. Only non-diabetics participants and participants with a CD4 count >200 cells/mm^3 will be eligible to participate which will further minimize risk for post-biopsy infection. Additionally, the study will have a safety officer ([name], a physician in the Infectious Diseases clinic). [name] will review

biopsy and exercise safety with [name] every 6 months.

Justification: Systemic IGF-I does not appear to be nearly as strongly linked to muscle adaption to exercise as local IGF-I at the level of the muscle. Additionally, skeletal muscle mitochondria are reflective of insults that may have occurred decades earlier, whereas mitochondrial studies obtained through peripheral blood would only reflect changes over a much shorter time period. Thus the muscle specimens provide a window into mechanisms well beyond what can be collected less invasively.

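### The non-diabetic restriction in the muscle-biopsy risk plan is not carried into any eligibility or biopsy-specific list, and the study's own diabetes criterion is inconsistent on HbA1c

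*Combined protocol and SAP*

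**What the plan says.** Three places in the combined protocol and SAP bear on whether a person with diabetes may have a muscle biopsy.

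- **Section IV.D, item 1 (Muscle biopsy), Plan to Minimize Risk.** A trained clinician is to perform the procedure on "participants who meet the biopsy-specific criteria listed above". The text then says "Only non-diabetics participants and participants with a CD4 count >200" cells/mm3 "will be eligible to participate which will further minimize risk for post-biopsy infection".
- **Section IV.B, main inclusion and exclusion criteria.** Because of interaction with the GH/IGF-I axis, the study excludes persons "with diabetes with a hemoglobin A1c >7%, on insulin, on GLP-1 analog, or DPP IV inhibitors". The next sentence reads "Well-controlled diabetics on other oral medications with hemoglobin A1c of 7.5 or less are eligible". The inclusion list separately requires "CD4 T-cell count greater than 200" cells/mm3.
- **Section IV.B, biopsy items at the end of the exclusion list.** "Participants on anticoagulants (clopidogrel, Coumadin, etc) will be excluded from the muscle biopsy", with an allowance for some short-acting agents if the treating physician approves. Then: "Aspirin and Non-steroidal anti-inflammatory agents are not exclusions but should be stopped 1 week prior to biopsy". Diabetes is not mentioned.

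Section IV.C describes those biopsied at procedure visit #1 only as volunteers: 36, or up to 46 if needed to secure 36 paired samples, with 18 HIV+ and 18 HIV-. The procedure text in IV.D, item 1 covers drug holds, fasting and technique, and adds no diabetes condition.

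**The concern.** The risk plan names a protection for participants in an invasive procedure: an incision through skin and fascia, made once before and once after the exercise programme. Anyone assessing risk from that paragraph would believe that no one with diabetes is biopsied. Anyone screening from the eligibility lists would find no such bar. The two operative parts of the protocol give different answers to the same question.

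There is a smaller scientific side. Change in muscle IGF-I mRNA is a primary outcome in the biopsy subset, and the protocol itself links diabetes to the GH/IGF-I axis. If the restriction were applied to some volunteers and not to others, the make-up of the biopsy groups could depend on who did the screening.

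**Working it through.** No formula decides this point, and the plan gives no figure to reproduce. The check is to trace the restriction through every place that governs biopsy eligibility.

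**1. Split the risk-plan sentence into its two conditions.**

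| Condition | Main criteria (IV.B) | Biopsy items (IV.B) | Visit schedule (IV.C) | Biopsy procedure text (IV.D, item 1) |
|---|---|---|---|---|
| CD4 above 200 | Present, as an inclusion criterion | Not needed | None | None |
| Non-diabetic | Absent; some people with diabetes are admitted | Absent | Absent | Absent |

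The CD4 condition is carried through. The diabetes condition appears only in the risk paragraph.

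**2. Suppose eligibility there means the whole study.** Take a person with diabetes whose HbA1c is 7% or lower, on an oral medication other than a DPP IV inhibitor and on neither insulin nor a GLP-1 analog. The IV.B exclusion does not reach this person and the following sentence admits them if well controlled. The risk plan says they are ineligible. This contradiction remains however the HbA1c thresholds are settled.

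**3. Suppose it means the biopsy only.** A narrower biopsy subset inside a broader study would be coherent. But the risk plan refers to criteria already listed, and the biopsy items in IV.B contain only an anticoagulant exclusion and a stopping instruction for aspirin and NSAIDs. The restriction is missing from the list it relies on.

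**4. Ask whether the main diabetes exclusion can stand in for the restriction.** It cannot. Its stated reason is the GH/IGF-I axis, not infection, and it leaves some people with diabetes in the study.

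**5. Set the two HbA1c statements side by side,** for a person with well-controlled diabetes on other oral medication:

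- 7% or lower: eligible under both sentences.
- Above 7% and up to 7.5%: excluded by the first sentence, eligible by the second.
- Above 7.5%: excluded by the first sentence, not admitted by the second.

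The middle band has no determinate answer, so it is unclear which people with diabetes can enter the study at all.

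**6. Scale.** The documents give no count of people with diabetes, so the number affected cannot be calculated. The only related figure is the risk section's overall biopsy infection rate, below 0.4% of cases. If cases are read as procedures:

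- 36 people biopsied twice: 72 procedures, 72 × 0.004 = 0.29.
- 46 at entry and 36 at completion: 82 procedures, 82 × 0.004 = 0.33.
- Upper limit, all 46 biopsied twice: 92 procedures, 92 × 0.004 = 0.37.

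Fewer than about 0.3 to 0.4 infections would thus be expected in all. That rate is not specific to people with diabetes, so it neither shows nor rules out a higher risk in them.

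**The case against.** The strongest reply is that the risk plan is current protocol text, sits in the biopsy section and states the restriction outright. Read as a biopsy rule, it can simply be followed, and the only defect is that IV.B does not repeat it. That is a fair reading. A reader might infer that the safeguard is not in force, or that people with diabetes will be biopsied. The documents do not support either. They show that the restriction has not been carried into the lists used for screening, so such a biopsy could happen.

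The protocol also has other protections: a trained clinician whose skills must be approved, observation after the procedure, a telephone check of the wound within 48 hours and a safety review every 6 months. These limit the consequences of an error, but none of them settles who is eligible.

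A reader might also infer that the muscle IGF-I comparison is biased. That would require people with diabetes to enrol, to volunteer for biopsy, to meet uneven application of the restriction and to be distributed unequally by HIV status. The documents give no data on any of these steps. The outcome in the biopsy subset is a paired change, which removes part of any stable difference between people, although Hypothesis 2b also compares levels at baseline and week 20. On the other side, the recruitment balancing (age, gender, BMI, smoking) and the two-way ANOVA for gene expression (timing, serostatus) do not include diabetes, so the plan would not correct an imbalance if one arose. It remains a possibility and no more.

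**Conclusion.** The inconsistency stands on either reading of the risk plan: a direct contradiction of IV.B if it means the whole study, or an omission from the biopsy criteria if it means the biopsy alone. The HbA1c conflict within IV.B is a second, separate fault, and it leaves open which people with diabetes can enter.

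The practical reach is limited to participants with diabetes among the 36 to 46 biopsied. Their number is unknown and may be zero. The point concerns participant safety and consistent eligibility. It does not alter the sample size, the power or the chair-rise analysis. The conclusion rests only on the current text of IV.B, IV.C and IV.D, with no assumption about diabetes prevalence or about infection risk in diabetes. It is worth correcting because two operative passages disagree on who may undergo an invasive procedure that is done twice.

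**What to change.** Reconcile three places so that they give one consistent rule:

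- the diabetes criterion in IV.B, including its two HbA1c thresholds;
- the biopsy-specific items in IV.B;
- the risk statement in IV.D, item 1.

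The biopsy conflict can be removed either by entering the diabetes restriction among the biopsy-specific items or by correcting the risk statement to match the people who may actually be biopsied. The wording should also say whether the statement governs the whole study or the biopsy only. Which diabetes rule and which HbA1c limit apply are clinical decisions for the investigators, and none is proposed here.

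The cost is about one line for the biopsy restriction and one for the HbA1c criterion, with no change to the design, sample size or analysis.
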